3.1.9 Participating participants MUST receive appropriate care and treatment for HIV infection, including antiretroviral medications, when clinically indicated and should be under the care of a physician experienced in HIV management. Participants will be eligible regardless of antiretroviral medication (including no antiretroviral medication) provided there is no intention to initiate therapy or the regimen has been stable for at least 4 weeks with no intention to change the regimen within 8 weeks following study entry. As study-specific (antiretroviral-

based) strata fill, however, only participants who are receiving the therapies eligible for the remaining open strata will be accrued.

- 3.1.10 Ability to understand and the willingness to sign a written informed consent document.
- 3.1.11 Participants must in the opinion of the investigator be capable of complying with this protocol.

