#### 5.3.1.2 Other medications

Participating participants MUST receive medically appropriate care and treatment for HIV infection, including antiretroviral medications when clinically indicated. Suspension or modification of an antiretroviral regimen during study participation will be permitted (after 8 weeks from study entry) at the discretion of the physician providing HIV care, provided the change and its rationale are carefully documented. However, due to potential differences in protocol therapy dosing associated with study stratification, therapeutic change to a ritonavir or cobicistat-containing antiretroviral regimen for a participant enrolled on a different study arm will necessitate immediate removal from the study.

Participants must be instructed to inform the investigators of the current or planned use or all other medications during the study (including prescription medications, over-the-counter medications, vitamins and herbal and nutritional supplements). It is the responsibility of the investigator to ensure that details regarding all medications are documented.

Bisphosphonates started prior to screening activities or initiated during the course of the study to control bone pain may be used with caution. **Please refer to [Section 6.1.15](#) for guidelines on prevention of osteonecrosis of the jaw (ONJ) when participants are receiving bisphosphonates.**

As the study will identify dose-limiting toxicities of this treatment regimen during the initial cycle of therapy, prophylactic growth factor (G-CSF) administration is not recommended. Based on observed toxicities, protocol-specified dose modification guidelines should be followed for subsequent therapy cycles. Management of anemia will be at the discretion of the treating physician,

No concurrent investigational agents are permitted.

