### **9.1 Screening/Baseline Evaluations**

Unless otherwise specified, the following evaluations must be performed within 1 week prior to start of therapy:

- 9.1.1 Complete medical history and physical examination, to include concurrent medications, medication history for eligibility (including ART regimen for 4 weeks prior to enrollment), vital signs, height, weight, performance status, CDC HIV risk categories, and history of AIDS defining conditions.
- 9.1.2 AIDS and Cancer Specimen Resource (ACSR) Consent for optional donation. It is required that AMC sites present the ACSR donation option to participants. (See [Appendix VII](#) for ACSR Informed Consent Form and [Appendix VI](#) for ACSR Specimen Preparation and Shipping Instructions).
- 9.1.3 CBC with differential and platelets, Serum chemistry: albumin, bicarbonate, BUN, calcium, chloride, creatinine, glucose, LDH, phosphorus, potassium, sodium, total protein and magnesium; Liver function tests: albumin, SGOT [AST], SGPT [ALT], total bilirubin, alkaline phosphatase.
- 9.1.4 Serum TSH, amylase, lipase
- 9.1.5 PT/INR and PTT
- 9.1.6 CD4+ and CD8+ lymphocyte counts and HIV viral load within 2 weeks prior to the start of therapy
- 9.1.7 Serum pregnancy test (for women of childbearing potential)
- 9.1.8 Urine dipstick or urinalysis. Proteinuria seen on urine dipstick or UA should warrant urine protein/creatinine ratio (UPCR) determination and management according to [Section 6.1.9](#).
- 9.1.9 Electrocardiogram (ECG) and QTc assessments within 4 weeks prior to the start of therapy.
- 9.1.10 CT scans to evaluate measurable disease within 4 weeks of start of therapy. CT will not be required for participants with KS.
- 9.1.11 ONLY in participants with known Kaposi sarcoma, chest X-ray to rule out pulmonary Kaposi's sarcoma. Pulmonary involvement must be asymptomatic or minimally symptomatic and not require systemic cytotoxic therapy in the judgment of the investigator. Participants with a positive chest X-ray or symptoms suggestive of pulmonary disease must have a chest CT performed before study entry.

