### **9.2 Evaluations During Treatment**

Evaluations may occur within a window of +/- 7 days. Assessments must occur on cycle 1, days 1, 8, 15, and 22, on Cycle 2, days 1 and 15, and on day 1 of all subsequent cycles as indicated in the Schedule of Evaluations ([Appendix I](#)).

- 9.2.1 Complete medical history and physical examination. To include vital signs, weight, performance status, adverse event evaluation). If hypertension (BP 140/90) is observed, decisions to decrease or hold the dose of study treatment must be based on BP readings taken by a medical professional and must be confirmed with a second measurement at least 5 minutes following the first measurement. (Refer to [Section 6.1.8](#) for management.)
- 9.2.2 CBC with differential and platelets, serum chemistry, amylase and lipase, and LFTs defined in [9.1.3](#).
- 9.2.3 Serum TSH. Testing should be performed every 4 weeks (every cycle) beginning Cycle 1 Day 1.
- 9.2.4 PT/INR and PTT. Testing should be performed every 8 weeks (2 cycles) beginning Cycle 1 Day 1.
- 9.2.5 CD4+ and CD8+ lymphocyte counts and HIV viral load. Samples will be obtained locally at time of Pharmacokinetic (PK) Specimen Collection on Cycle 1, Day 22, and at 12 week intervals while on study therapy.
- 9.2.6 Urine dipstick or urinalysis. Proteinuria seen on urine dipstick or UA should warrant urine protein/creatinine ratio (UPCR) determination and management according to [Section 6.1.9](#).
- 9.2.7 ECG and QTc assessments will be performed weekly during the first cycle of therapy, and day 1 of all subsequent cycles. Additional ECGs will be performed as indicated in [Section 6.1.16](#) (refer to [Appendix IX](#) for a list of drugs that may cause QTc prolongation).
- 9.2.8 CT scan for tumor measurement performed after every 2 cycles (every 8 weeks) of therapy for participants with solid tumors. Participants with cutaneous KS will not require CT scans.
- 9.2.9 KS participants will be evaluated for response after every other cycle according to the requirements in [Section 11.2](#). Chest x-ray will be performed as clinically indicated.
- 9.2.10 The participant will be given a copy of the participant diary to complete. Collect diary upon completion.
- 9.2.11 Correlative Studies (See [Section 10.0](#))

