### **12.4 Analysis of Secondary Endpoints**

Secondary endpoints for this study include response rates and effects of therapy on HIV viral load and CD4+ and CD8+ cell counts, as well as the results of pharmacokinetic studies. For participants with measurable disease, response evaluations will occur at 2 cycle intervals via RECIST 1.1. Study treatment may continue indefinitely until one of the following criteria applies: 1) unacceptable toxicity (including DLT in cycle 1); 2) progressive disease; or 3) participant withdrawal or removal.

To investigate possible pharmacokinetic interactions between cabozantinib and antiretroviral therapy in persons with HIV infection, pharmacokinetic analysis calculations will be conducted using WinNonlin (Pharsight Corporation, Mountain View, CA) with noncompartmental or compartmental methods. Relevant pharmacokinetic parameters will be computed for cabozantinib and relevant metabolites. The pharmacokinetic variables will be tabulated and descriptive statistics (e.g., geometric means and coefficients of variation) calculated for each dose level. Pharmacokinetic parameters (i.e.,  $T_{1/2}$ , Cl, and AUC) will be compared across relevant antiretroviral therapies using nonparametric statistical testing techniques. Concentrations obtained from the time of disease progression and the time of a DLT or other persistent and severe toxicity will be treated as independent samples and summarized in a descriptive manner. Correlations with toxicity and efficacy will be assessed using nonparametric statistical testing techniques. Significance for comparisons will be at the  $p<0.05$  level.

To investigate the effects of cabozantinib on participant immune status and HIV viral load, trends in CD4+ and CD8+ counts and viral load determinations during trial participation will be evaluated. A repeated measures analysis of variance will be used to assess the effect of cabozantinib on CD4+ and CD8+ cell counts and HIV viral loads across time points. Analyses will be done per stratum, where the data are sufficient. If the data do not meet the assumptions of normality, Friedman's test, the nonparametric analogue to a repeated measures analysis of variance, will be used.

Collectively and over each stratum, binomial proportions and their 95% confidence intervals will be used to preliminarily assess response rates for single agent cabozantinib in malignancies for which at least 4 participants have been enrolled.

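### Section 12.4 credits any trend in CD4+, CD8+ and viral load to cabozantinib and makes no use of the ART-change record

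*Combined protocol and SAP*

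**What the plan says.** **Analysis (Section 12.4).** The plan says that "trends in CD4+ and CD8+ counts and viral load determinations during trial participation will be evaluated" and that "A repeated measures analysis of variance will be used to assess the effect of cabozantinib on CD4+ and CD8+ cell counts", with viral load handled in the same way. The fallback is rank-based: "If the data do not meet the assumptions of normality, Friedman's test, the nonparametric analogue to a repeated measures analysis of variance, will be used". The one subdivision is this: "Analyses will be done per stratum, where the data are sufficient". No ART term, censoring rule or sensitivity analysis is given.

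**Entry (Section 3.1.9).** Any ART status is accepted provided that "there is no intention to initiate therapy or the regimen has been stable for at least 4 weeks", with no change intended in the 8 weeks after entry. No minimum time since stopping ART is set. Stratum C takes participants on other regimens together with those on none (Section 12.3).

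**On study (Section 5.3.1.2).** "Suspension or modification of an antiretroviral regimen during study participation will be permitted (after 8 weeks from study entry"), at the HIV physician's discretion, and the change and its reason must be documented. Only a switch to ritonavir or cobicistat by a participant from another stratum leads to removal.

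**Sampling.** The markers are measured at baseline, then "on Cycle 1, Day 22, and at 12 week intervals while on study therapy" (Section 9.2.5), and at discontinuation (Sections 9.3.3 and 10.1.2).

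**ART history (Section 9.1.1).** The baseline visit takes "medication history for eligibility (including ART regimen for 4 weeks prior to enrollment"). No start date for the current regimen, or stop date for the last one, is asked for.

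**The concern.** Every participant receives cabozantinib, so the time effect in the ANOVA cannot separate the drug from anything else that changes over the same weeks. ART is the obvious candidate, because CD4+ count and viral load are the markers by which HIV control is followed. A participant who entered soon after starting or stopping ART may still be moving towards a new level. One who suspends or changes ART after week 8 may move later. Either movement enters the estimate of what Section 12.4 calls the effect of cabozantinib.

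What is at stake is the answer to objective 1.2.2. Section 2.6.2 does not anticipate an effect on immune reconstitution, so a few ART-driven shifts could decide the result in either direction in groups this small.

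**Working it through.** **1. The plan's own figures.** Section 12.2 expects 4 to 18 participants in Stratum A, 6 to 18 in B and 6 in C. The sums are 4 + 6 + 6 = 16 and 18 + 18 + 6 = 42, which match the stated range of 16 to 42. No SD, effect size or rate of ART change is given for this analysis, so everything from step 3 on rests on assumed values.

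**2. Sampling times against the ART rules.**

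| Value | Position relative to week 8 |
|---|---|
| Baseline | Before treatment; may be 4 weeks into a regimen, or any time after stopping |
| Cycle 1 Day 22 | Before week 8; covered by the 8-week rule |
| Weeks 12, 24, ... | All after week 8; can follow a permitted change |
| Discontinuation | Either side, depending on when treatment ends |

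**3. Bias in the mean.** If k of n participants shift by d log10 because of ART, the mean moves by (k/n) × d. For 1 of 6:
- d = 2: 2/6 = 0.33
- d = 3: 3/6 = 0.50
- d = 4: 4/6 = 0.67

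**4. False-positive rate of the planned tests.** Simulation with no drug effect; four time points (baseline, week 3, week 12, week 24); assumed within-person SD 0.3 log10; the shift is present from week 12; alpha 0.05; 3,000 runs. Each cell gives the rate for a shift of 1 / 2 log10.

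| Participants shifting | ANOVA | Friedman |
|---|---|---|
| 1 of 6 | 3.9% / 1.3% | 3.5% / 4.0% |
| 2 of 6 | 13.5% / 14.2% | 8.1% / 7.9% |
| 3 of 6 | 45% / 78% | 20.5% / 20% |
| 4 of 12 | 53% / 92% | 19% / 21% |
| 3 of 18 | 19% / 42% | 8.7% / 10% |

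With nobody shifting, the rates were 4.7% to 5.7% (ANOVA) and 3.9% to 5.5% (Friedman) for n = 6, 12 and 18.

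**5. The opposite error.** With n = 6 and an assumed true drug effect of 0.5 log10 from Day 22, ANOVA power is 74% when nobody changes ART. One rebound in the same direction as the drug effect lowers it to 48% (2 log10) or 19% (3 log10); a 1 log10 rebound costs nothing material. One shift of 2 log10 in the opposite direction lowers it to 2%. The outlier inflates the error variance. Friedman's test, being rank-based, does not lose power when the outlier lies in the direction of the drug effect.

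**6. Recent starters.** Suppose viral load falls a further 0.5 log10 by week 3 and 1.0 by week 12. The ANOVA then rejects in 3.8% of runs (1 of 6), 12% (2 of 6) and 41% (4 of 12). With 2 of 6, the Day 22 mean is already off by 2/6 × 0.5 = 0.17 log10, so that contrast is not immune either.

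**The case against.** Several safeguards exist. ART users need 4 stable weeks and no intended change for 8 more. HIV care must be appropriate throughout, so free suspension of ART is not the expected course. One type of switch leads to removal. These protect Day 22, and also a discontinuation sample taken before week 8. They do not protect the later series.

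A reader might infer that recent starters and stoppers can never be identified. The documents do not support that. Section 9.1.1 asks for a full history with concurrent medications, Section 5.3 requires the case report form to capture all other drugs, and on-study changes are documented. The gap is narrower: no start or stop date is required, and Section 12.4 does not call on the record.

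A reader might also infer that one viral rebound in a stratum of 6 would be declared harm by the planned test. It would not. With one participant shifting, both tests stay at or below about 5%. Only the mean is biased.

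Finally, dropping values after an ART change is not neutral. Section 2.6.2 names an interaction with antiretrovirals as a conceivable route of effect, so a change prompted by lost viral control could itself be a drug signal. Restricting the main result to Day 22 would also shrink the question to three weeks. Both objections stand, and they argue for showing two analyses rather than replacing one with the other.

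**Conclusion.** The point holds as a gap in the analysis plan. Followed as written, Section 12.4 can attribute ART-driven movement to cabozantinib, or miss a real drug effect because of it. The bias in the mean is the share of participants affected times their shift. Over-rejection needs several participants moving the same way: about 14% with 2 of 6, and 53% to 92% with 4 of 12, for assumed shifts of 1 to 2 log10 and an SD of 0.3. How often ART would change, and by how much the markers would move, cannot be taken from the documents. Nor do they give a figure showing that ART effects exceed drug effects.

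Stratum-wise analysis does not solve this, because strata follow the regimen at entry and Stratum C mixes treated and untreated participants. The endpoint is secondary, and no escalation decision or MTD depends on it. The passages compared concern CD4+, CD8+ and viral load only; they support no inference about Kaposi sarcoma response.

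**What to change.** In Section 12.4:
- Flag each participant's first on-study start, stop or change of ART.
- Prespecify the repeated-measures analysis twice: with all values, and with values before that first change only. List the later values separately with the reason for the change.
- Summarise participants on no ART apart from those on ART, descriptively where numbers are small (Stratum C is expected to hold 6).
- Report baseline to Cycle 1 Day 22 as a supporting contrast.
- Describe results as change during treatment, not as the effect of cabozantinib.

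In Section 9.1.1, record the start date of the current regimen or the stop date of the last one, so that recent starters and stoppers can be listed.

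The cost is one or two date fields, some plan wording, and fewer values at later time points in the restricted analysis. Eligibility and HIV care stay as they are. Fixing the rule before results are seen also avoids choosing afterwards which values count.

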### **9.3 Final Evaluations, Off Treatment (within 7 days of last treatment)**

At the completion of all follow-up evaluations, the Off Protocol Treatment Summary Form should be completed in AdvantageEDC.

- 9.3.1 Complete medical history and physical examination. To include vital signs, weight, performance status, adverse event evaluation)
- 9.3.2 CBC with differential and platelets, serum chemistry, and LFTs defined in [9.1.3](#).
- 9.3.3 CD4+ and CD8+ lymphocyte counts and HIV viral load
- 9.3.4 Serum TSH, amylase, lipase

- 9.3.5 PT/INR and PTT
- 9.3.6 Urine dipstick or urinalysis. Proteinuria seen on urine dipstick or UA should warrant urine protein/creatinine ratio (UPCR) determination and management according to [Section 6.1.9](#).
- 9.3.7 Electrocardiogram (ECG) and QTc assessments
- 9.3.8 CT scan for tumor measurement. Radiologic documentation must be provided for participants removed from study for progressive disease. Participants with cutaneous Kaposi sarcoma will not require CT scans and will be evaluated for response according to [Section 11.2](#). Chest x-ray will be performed as clinically indicated.
- 9.3.9 Collect diary upon completion.

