This trial will include participants with HIV infection, provided participants are receiving appropriate treatment and followed by physicians monitoring their care. While it is not anticipated that cabozantinib will alter immune reconstitution in participants, HIV viral load and CD4+ cell counts will be monitored to ensure adequate control of the participant's HIV infection. Samples will be obtained locally at baseline, at time of Pharmacokinetic (PK) Specimen Collection on Cycle 1, Day 22, and at 12 week intervals while on study therapy, and at time of study discontinuation.

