### 10.2.2 To investigate the effects of therapy on participant immune status and HIV viral load.

#### 10.2.2.1 Collection of specimens

All participants will have baseline and follow-up evaluations of CD4+ and CD8+ lymphocyte counts and HIV viral load on Cycle 1, Day 22 (along with Pharmacokinetic (PK) Specimen collection) and at every 12 weeks during study participation as part of standard HIV care. Participants will also have these evaluations performed at time of study discontinuation.

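### The repeated measures ANOVA and Friedman's test planned for CD4+, CD8+ and HIV viral load by default drop participants with incomplete visits, and no rule covers the discontinuation sample or values below the assay limit

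*Combined protocol and SAP*

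**What the plan says.** Objective 1.2.2 concerns the effect of therapy on immune status and HIV viral load. For its analysis, Section 12.4 states: "A repeated measures analysis of variance will be used to assess the effect of cabozantinib on CD4+ and CD8+ cell counts" and HIV viral load across time points. The fallback is conditional: "If the data do not meet the assumptions of normality, Friedman's test" is used instead, described as "the nonparametric analogue to a repeated measures analysis of variance". On strata it adds: "Analyses will be done per stratum, where the data are sufficient". It does not define sufficient, list the time points, name an analysis set, say how missing visits are treated, or mention a mixed model.

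Section 10.1.2 schedules sampling at baseline, at Cycle 1 Day 22, "and at 12 week intervals while on study therapy, and at time of study discontinuation". Section 10.2.2.1 agrees: "at every 12 weeks during study participation as part of standard HIV care", and "Participants will also have these evaluations performed at time of study discontinuation". Section 9.3 places the off-treatment evaluations, which include these three measures, no more than a week after the final dose. Testing is done at local laboratories (Section 10.2.2.2). No detection limit, viral-load scale or rule for values below a limit is given.

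**The concern.** Classical repeated measures ANOVA and Friedman's test work on complete blocks: a participant with a gap at any included time point leaves the analysis. This design will produce gaps. Treatment has no fixed length, so participants will have different numbers of 12-weekly samples. Disease is first reassessed at about 8 weeks (Sections 9.2.8, 9.2.9 and 11.0), and progression ends treatment (Section 5.4). Someone who progresses at the first assessment will therefore normally have no week-12 value. Absence from the week-12 comparison is thus tied to progression and toxicity rather than to chance.

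The discontinuation sample is meant to supply a late value for these participants. It comes at a different time for each of them, and Section 12.4 does not say where it enters.

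At stake is the reading of objective 1.2.2. A comparison limited to participants still on drug could differ from one in everyone treated, and samples that the protocol requires could go unused.

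**Working it through.** **The plan's own figure.** Section 12.2 expects 4 to 18 participants in Stratum A, 6 to 18 in B and 6 in C. The sums are 4 + 6 + 6 = 16 and 18 + 18 + 6 = 42, which match the stated 16 to 42. The plan gives no effect size, standard deviation, power or dropout rate for this analysis, so there is nothing further to reproduce.

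**Share with complete visits.** The documents give no time on treatment for this trial. I assume exponential time on drug and no missed samples while on it, so that

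share complete to week t = 0.5^(t / median).

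Day 22 is t = 3 weeks. For example, at a median of 8 weeks and t = 12, 0.5^(12/8) = 0.5^1.5 = 0.35.

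| Assumed median (weeks) | To Day 22 | To week 12 | To week 24 |
|---|---|---|---|
| 8 | 77% | 35% | 12.5% |
| 12 | 84% | 50% | 25% |
| 16 | 88% | 59% | 35% |
| 24 | 92% | 71% | 50% |
| 36 | 94% | 79% | 63% |
| 52 | 96% | 85% | 73% |

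As counts to week 12, this is 14.8 to 35.8 of 42, 5.7 to 13.6 of 16, and 2.1 to 5.1 of a stratum of 6. To week 24, a stratum of 6 keeps 0.8 to 4.4. The loss depends heavily on which visits are included, and the plan does not say.

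**Could dropping early leavers matter?** One simulated scenario used 42 participants, 300 runs, a true change of −0.50 and, by assumption, dropout that is likelier after a fall. At nominal median times on drug of 12 and 24 weeks, about 11 and 20 participants were complete to week 24. The complete-case estimates were −0.09 and −0.23. A mixed model on all observed visits gave −0.51 in both cases. Some model fits gave convergence warnings. The direction was built in by the dropout assumption: dropout unrelated to the measure would remove the bias, and the opposite relation would reverse it. The scenario shows that bias is possible, not that it will occur here.

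**Values below the assay limit.** Friedman's test uses ranks within each participant, so values below a common limit become ties. In a worked example with 6 participants, three different substituted values at or below the limit gave the same statistic (7.11, p = 0.029). A simulation assumed three time points, a limit of 50 copies/mL and 50% to 95% of participants suppressed (2,000 runs per setting):

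- Type I error was 0.011 to 0.036 at n = 6, 0.031 to 0.039 at n = 12, and 0.034 to 0.050 at n = 18 and 42.
- All values were tied, leaving the test undefined, in 0.2% to 13% of runs at n = 6 and in at most 1.5% at n = 12 or more.

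The test is therefore conservative in very small strata but not invalid. The ANOVA has no such protection: its result depends on the number substituted for an undetectable value. Even ranks are affected if the local limit changes within a participant.

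**The case against.** The strongest reply is that Section 12.4 is brief rather than wrong. It prescribes no complete-case rule, and a repeated measures analysis can be fitted as a mixed model. It promises to evaluate trends during participation without requiring complete visits, and it anticipates sparse strata. Baseline, Day 22 and end of treatment would form a common, event-based set of occasions that many early leavers could complete. The protocol expects no effect on immune reconstitution (Sections 2.6.2 and 10.1.2), and no dose decision uses this analysis.

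Much of this stands, and it rules out several stronger readings that a reader might infer:

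- **That the analysis will rest on a minority of participants.** No time-on-drug figure supports this. Half or more reach week 12 at any assumed median of 12 weeks or longer, and at least 77% reach Day 22 throughout the range.
- **That discontinuation samples cannot be analysed.** They can; the plan simply does not say how.
- **That undetectable viral loads defeat the plan.** The fallback handles them as ties under a common limit. How often they will occur is also unknown, since Section 3.1.9 admits participants with or without antiretrovirals.
- **That the result is biased toward no effect.** Nothing in the documents shows that early leavers have immune decline.

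The reply does not remove the default. The methods are named without qualification, and calling Friedman's test the analogue of the ANOVA suggests the classical form. Even if the ANOVA were fitted as a mixed model, the fallback would still need complete blocks.

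**Conclusion.** The concern holds as a choice of method that suits this sampling scheme poorly, together with missing rules. Applied in their standard form, the named analyses leave early leavers out of later-visit comparisons and give the discontinuation sample no defined role. Under assumed exponential time on drug with medians of 8 to 52 weeks, 35% to 85% would be complete to week 12, and 77% to 96% to Day 22; the documents do not narrow this range. Bias would arise if leaving is related to immune or viral change, but neither its direction nor its size is established. The missing scale and censoring rule matter for the ANOVA on viral load and wherever local assay limits differ.

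Severity is minor to moderate. This is a secondary objective in a phase I dose-escalation trial, and MTD determination does not depend on it.

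**What to change.** Replace the ANOVA/Friedman sentences in Section 12.4 with a linear mixed model for each measure:

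- **Model:** a random participant intercept and actual time since first dose, with the form of the time effect stated in advance.
- **Data:** every available sample, including Day 22 and discontinuation.
- **Strata:** a pooled fit with stratum as a covariate, and separate fits only where data allow, with a stated minimum.
- **CD4+ and CD8+:** a log or square-root scale, named in advance.
- **Viral load:** log10 scale, with values below the limit left-censored at the limit of the assay used. Where that cannot be estimated, as may happen in a stratum of 6 with mostly undetectable values, report the proportion above the limit at each visit.
- **ART changes:** Section 5.3.1.2 permits these after 8 weeks, before the first 12-weekly sample, so identify samples taken after a change when reporting.

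The cost is revised wording and a little more programming, with no new data. The model assumes that missing values are missing at random given what was observed. This cannot be verified, but it is more plausible when the discontinuation sample is included.

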### 12.2 Sample Size/Accrual Rate

No formal statistical hypothesis testing is planned for the primary analysis. Sample size estimates are in agreement with those of a traditional phase I dose escalation 3+3 design. It is expected that the study will enroll approximately 16 to 42 participants across potentially three Strata (Ritonavir or Cobicistat (CYP3A4 inhibitor)-containing HAART [**Stratum A**]; Efavirenz or Etravirine (CYP3A4 inducer)-containing HAART [**Stratum B**]; and Others [**Stratum C**]). Among the expected 16 to 42 enrolled participants, 4 to 18 are expected to be enrolled in Stratum A, 6 to 18 are expected to be enrolled in Stratum B, and 6 participants are expected to be enrolled in Stratum C.

Following the determination of the MTD in each stratum, the MTD dose level for each stratum may be expanded to 6 to 12 participants according to participant availability for further characterization of toxicity, preliminary assessment of response and additional translational study samples. A decision to halt accrual because of lack of participant availability will be at the discretion of CTEP investigators.

The estimated accrual rate for this study is 1 - 2 participants/month.

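### For CD4+, CD8+ and HIV viral load, Section 12.4 names only an omnibus test; without an estimate of change, an interval or a count of virologic failures, the result cannot show how much worsening is excluded

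*Combined protocol and SAP*

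**What the plan says.** Objective 1.2.2 is to investigate the effect of therapy on immune status and viral load. Section 12.4 first says that "trends in CD4+ and CD8+ counts and viral load determinations during trial participation will be evaluated", without naming a statistic. It then gives the method: "A repeated measures analysis of variance will be used to assess the effect of cabozantinib on CD4+ and CD8+ cell counts" and on viral load, across time points. The scope is conditional: "Analyses will be done per stratum, where the data are sufficient". Neither the meaning of sufficient nor a fallback to pooled data is given. For non-normal data, "Friedman's test, the nonparametric analogue to a repeated measures analysis of variance, will be used".

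Section 10.1.2 states the expectation that "it is not anticipated that cabozantinib will alter immune reconstitution in participants" and gives adequate HIV control as the reason for monitoring. Readings are scheduled at baseline, Cycle 1 Day 22, every 12 weeks and at discontinuation (Section 10.2.2 and Appendix I).

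Section 12.2 gives the sizes: "4 to 18 are expected to be enrolled in Stratum A, 6 to 18 are expected to be enrolled in Stratum B", and 6 in Stratum C. The MTD level in each stratum may be expanded to 6 to 12.

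For comparison, Section 12.4 plans binomial proportions with 95% confidence intervals for response, both overall and by stratum, and geometric means with coefficients of variation for PK parameters.

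**The concern.** The question is one of safety: has immune status or HIV control worsened, and by how much? An omnibus test across time points has no direction and returns no size. It can reject equality, but failing to reject does not tell a reader which amounts of worsening are ruled out. With the expected stratum sizes it will often fail to reject even when a moderate worsening is real.

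Viral load has a further mismatch. Control is a matter for each participant, and the harm of interest is a few people losing suppression. A comparison of means or rank sums over time is not built to show that.

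Two things raise the stakes. Section 2.5 presents the trial as a basis for including people with HIV in later cabozantinib studies. The PK plan in Section 10.1.1 measures cabozantinib and its metabolites, not antiretroviral concentrations, so these endpoints carry the evidence on whether cabozantinib undermines antiretroviral therapy.

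**Working it through.** **Inputs from the documents.** Stratum sizes 4–18, 6–18 and 6. The sentence starting "Significance for comparisons will be at the" sets p<0.05; it stands in the PK paragraph of Section 12.4 and is assumed here to apply to these tests as well.

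**Assumptions.** The documents give no effect size, SD, margin or dropout rate for these endpoints. I assume three readings (baseline, Day 22, week 12), complete data and compound symmetry. The mean worsening is d, in units of the SD of within-person change.

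**1. The plan's own figure.** 4+6+6 = 16 and 18+18+6 = 42, which matches the stated 16 to 42.

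**2. Power for a mean fall.** With the SD of change set to 1, the residual variance is 1/2. For a sustained fall (0, −d, −d), the squared deviations of the means sum to (2/3)d². The noncentrality is therefore n·(2/3)d²/(1/2) = (4/3)nd², with 2 and 2(n−1) degrees of freedom. For a gradual fall (0, −d/2, −d) it is nd². At d = 0.5, sustained, the noncentrality is 2, 4 and 6 at n = 6, 12 and 18. Friedman's test was simulated for the same fall (20,000 runs, chi-square reference).

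| n | ANOVA misses | Friedman misses |
|---|---|---|
| 6 | 82% | 84% |
| 12 | 63% | 69% |
| 18 | 46% | 60% |

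Other simulation runs agree within about 3 points. At d = 0.8, ANOVA power is 31% (gradual) to 40% (sustained) at n = 6, but 84% to 93% at n = 18.

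**3. Viral load, with m of n participants rebounding at the last reading and everyone else tied at the assay limit.**

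- *Friedman.* A rebounder has ranks 1.5, 1.5, 3; the others have 2, 2, 2. The rank sums differ from 2n by −m/2, −m/2 and +m, with squares summing to 1.5m². The within-participant squares sum to 1.5m. The tie-corrected statistic is 2·1.5m²/(1.5m) = 2m on 2 df, so p = exp(−m), whatever n is. That gives 0.37 (m = 1), 0.135 (m = 2) and 0.0498 (m = 3). The exact permutation p-value is 3/3^m, or 0.33 for m = 2 and 0.11 for m = 3.
- *ANOVA.* With equal rebounds, F = m(n−1)/(n−m), and the height of the rebound cancels. For m = 2, F is 2.5, 2.2 and 2.125 at n = 6, 12 and 18, with p = 0.132, 0.135 and 0.135.

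So two of six participants losing control (33%) would be non-significant by either test, however large the rebounds.

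**4. What an estimate would give.** The 95% half-width for a mean change is t(0.975, n−1)/√n: 1.05 SD at n = 6, 0.64 at 12, 0.50 at 18 and 0.31 at 42. With no rebounds, the one-sided 95% upper bound on the rebound rate is 1 − 0.05^(1/n): 39% at 6, 22% at 12, 15% at 18 and 6.9% at 42.

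**The case against.** The strongest reply is that the harm is inferred. A reader might conclude that the plan will treat p>0.05 as proof of no effect. The documents do not say so: Sections 2.6.2 and 10.1.2 state an expectation and a monitoring purpose, not a decision rule. That reply stands.

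A reader might also infer that the omnibus test is all that will be looked at. Section 12.4 says that trends will be evaluated, and it makes per-stratum analysis conditional on sufficient data, so a test in a stratum of 4 may never be run. This stands too, but it does not supply a named summary.

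A third tempting reading is that the test would usually miss harm. That depends on size and effect. In a stratum of 18, ANOVA detects a sustained 0.5 SD fall slightly more often than not and a 0.8 SD fall 84–93% of the time. Stratum C could also grow beyond 6 through the MTD expansion.

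Last, one might claim that Friedman's test stays blind to a minority losing control even in large samples. If 20% rebound by 2 log10 at both on-treatment visits and everyone else carries small untied noise, it misses about 87% at n = 18 and 71–72% at n = 42. With the others tied at the assay limit, the misses fall to roughly 26–44% at n = 18 and about 1% at n = 42. The claim rests on the noise assumption and is not made here.

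It is also fair to say that a formal margin would be heavy for a secondary endpoint in a trial with no formal testing of its primary endpoint, that reporting Day 22 alone would neglect slower change, and that pooling mixes different doses and antiretroviral regimens. The fix below allows for these points.

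**Conclusion.** The concern holds in limited form. The only named method for CD4+, CD8+ and viral load is a test of equality, with no estimate of change, interval or count of virologic failures, while other secondary endpoints in the same section do get intervals or descriptive statistics. That gap is in the text and needs no assumption.

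Its size depends on assumptions. For a sustained 0.5 SD fall with three complete readings, the tests miss about 82–84% at n = 6, 63–70% at n = 12 and 45–60% at n = 18. Dropout before week 12 would raise these in a complete-case analysis. The result that two rebounds are non-significant at n = 6, 12 or 18 assumes that the others are tied and that the rebounds come at the last reading.

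The documents do not support saying that the trial will declare no effect by default, or that the method fails at every stratum size. This is a cheap improvement to a secondary analysis and leaves the MTD determination untouched.

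**What to change.** In Section 12.4:

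1. Report within-participant change from baseline in CD4+, CD8+ and log10 viral load at Cycle 1 Day 22 and at each 12-weekly reading, with 95% confidence intervals, by stratum. As a supportive summary, give the same over all strata with adjustment for stratum.
2. Report the number of participants suppressed at baseline whose viral load rebounds above a threshold fixed in advance, with an exact upper bound. Use only those suppressed at baseline as the denominator: eligibility does not require suppression, and Stratum C admits people on no antiretroviral therapy.
3. Keep the ANOVA or Friedman p-value as supportive, and state that a non-significant result is not evidence of no effect.

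The cost is a few sentences and a little more analysis, with no new visits or samples. The drawback is that the intervals will be wide and the result often inconclusive: with no rebounds the upper bound is still 39% for 6 suppressed participants and 7% for 42. The denominators will be smaller, and the bounds wider, wherever some participants are not suppressed at baseline.
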